#### 5.1.1. Additional Summaries

Additional summaries will be provided to support the clinical trial results summary part of European Union Clinical Trial Regulation (EU CTR) reporting along with the disposition summary table described in [Section 5.1](#). These include participants enrollment breakdown by country, the overall participants enrollment breakdown by age group and the overall participants gender breakdown.

### 5.2. Protocol Deviations

The number and percentage of participants with significant protocol deviations will be summarized by deviation category, study part, dose cohort, and overall, for the Safety Set.

Participants will be counted once within each deviation category regardless of how many deviations they have in that category. A review of the protocol deviations will be performed prior to database lock.

All protocol deviations will also be presented in a data listing for the Screened Set.

## 6. Demography and Baseline Characteristics

### 6.1. Demography

Demography data will be summarized by study part, dose cohort, and overall. Individual participant listings will be provided to support the summary table.

Age (year), weight (kg), height (cm) and body mass index (BMI) will be summarized using descriptive statistics (i.e., n, mean, standard deviation, median, minimum, and maximum). Age

category (year), race, sex, ethnicity, and other categorical variables (see list below) will be summarized with frequency tabulations.

Other characteristics include:

- Age group (<65 years, ≥65 years);
- Region (Europe, North America, Latin America);
- Screening hemoglobin level;
- Screening platelet count;
- Screening GCase activity levels (Plasma and DBS);
- Screening GCase concentration;
- Screening chitotriosidase activity (DBS);
- Screening Lyso-Gb1 (Plasma and DBS);
- Screening liver volume (multiples of normal);
- Screening spleen volume (multiples of normal);
- Screening bone mineral density T-score (Lumbar spine and Hips);
- Screening bone mineral density Z -score (Lumbar spine and Hips);
- Screening pulse rate (beats per minute);
- Screening blood pressure (mmHg);
- Screening respiratory rate (breaths per minute);
- Screening body temperature (°C);

## **6.2. Baseline Characteristics**

Baseline Gaucher disease characteristics collected at screening, including age at diagnosis, genotyping (genes encoding for  $\beta$ -glucocerebrosidase (GBA1) and CHIT1) results, Gaucher disease severity (GD-DS3), and ERT/SRT history, will be summarized descriptively by study part, dose cohort, and overall. A listing of the baseline Gaucher disease characteristics including the date symptoms began will be presented.

Baseline characteristics summary table will also be used for clinical trial results summary part of the EU CTR reporting.

## **6.3. Medical History**

### **6.3.1. General Medical History**

Medical history will be coded using the Medical Dictionary for Regulatory Activities (MedDRA) Version 26.1 or higher.

The number and percentage of participants with any general medical history not related to Gaucher disease will be summarized overall and for each system organ class (SOC) and preferred term for each study part, dose cohort, and overall. Percentages will be calculated based on number of participants in the Safety Set. All medical history data will be presented in a listing.

### **6.3.2. Gaucher Disease Medical History**

Medical history related to Gaucher disease will be coded using the MedDRA dictionary (Version 26.1 or higher).

Medical history related to Gaucher disease will be summarized by SOC and preferred term for each study part, dose cohort, and overall. Medical history data related to Gaucher disease will be presented in a listing.

## **6.4. Inclusion and Exclusion Criteria**

The inclusion and exclusion criteria are listed in the protocol. All inclusion/exclusion information will be included in a by-participant listing for the Screened Set. For participants who did not satisfy these criteria, the criteria numbers will be listed with the deviation.

## **7. Treatments and Medications**

### **7.1. Gaucher Disease Therapy**

ERT/SRT use will be summarized using Anatomical Therapeutic Chemical (ATC) Level 4 (if this is not available, the closest ATC level will be used) by preferred term, study part, dose cohort, and overall. Rules on imputation of incomplete dates are found in [Section 4.1](#). All ERT/SRT data will be presented in a listing.

### **7.2. Prior and Concomitant Medications**

All medications will be coded according to the World Health Organization (WHO Drug dated September 2023 or later) Drug Dictionary and summarized using the ATC class Level 4 (if this is not available, the closest ATC level will be used) and preferred term. All prior and concomitant medications information will be presented in a listing.

#### **7.2.1. Prior Medications**

Prior treatment includes all non-Gaucher disease therapy received from 30 days prior to the initial informed consent up until the time of IMP infusion.

Prior medications will be summarized using ATC Level 4 (if this is not available, the closest ATC level will be used) by preferred term, study part, dose cohort, and overall. Rules on imputation of incomplete dates are found in [Section 4.1](#).

#### **7.2.2. Concomitant Medications**

Concomitant treatment refers to all treatment taken between the date of IMP infusion and the end of study visit (Week 38 for all participants excluding US and Month 24 for participants in the US only) inclusive.

Concomitant medication includes prescription and non-prescription medication and herbal treatments. Concomitant medication also includes immunosuppressants used as part of an immune management and monitoring regimen. If immunosuppressant drugs are used, tacrolimus levels will be monitored, and data will be presented (see [Section 9.6.2](#)).

Concomitant medications will be summarized using ATC Level 4 (if this is not available, the closest ATC level will be used) by preferred term, study part, dose cohort, and overall. Rules on imputation of incomplete dates are found in [Section 4.1](#).

In addition, participants immunosuppressant drug dose levels will be plotted over time for all participants who received at least one dose of any immunosuppressant drugs described in the protocol.

#### **7.2.3. Procedures**

Data from prior and concomitant procedures form (procedure name, date, reason or indication, and associated AEs or medical history) will be presented in a listing.

### **7.3. Study Treatments**

#### **7.3.1. IMP Infusion**

IMP infusion data (i.e., total amount of IMP received, if infusion is interrupted, any related reactions) will be summarized by study part, dose cohort, and overall. IMP infusion data will be presented in a listing.

#### **7.3.2. Treatment Compliance and Modifications**

A single IMP infusion will be administered to the participant at the study site by trained study staff. All IMP will be tracked and accounted for at the investigational site following receipt, dispensing and administration to participant, and ultimately including destruction or return to the Sponsor. Therefore, no analysis of compliance is planned.

### **8. Efficacy Analysis**

Summaries and analysis of efficacy endpoints will be performed using the Safety Set unless otherwise specified.

Primary endpoints and secondary efficacy endpoints descriptive summaries will also be used to support the clinical trial results summary part of the EU CTR reporting.

#### **8.1. Derivations of Efficacy Endpoints**

Participant data will be entered into Rave (Medidata's electronic data capture system), but the following endpoints require additional programming to be calculated from the entered data.

##### **8.1.1. Health-related Quality of Life (SF-36 Score)**

The eight SF-36 health domain scores (physical functioning, role-physical, bodily pain, general health, vitality, social functioning, role emotional, mental health) and two component summary scores (physical and mental) will be derived according to the QualityMetric SF-36v2 Health Survey Third Edition User's Manual. Absolute values and changes from baseline in the health domain scores and component summary scores will be summarized.

#### **8.2. Primary Endpoint**

The primary endpoint for this study is to assess the safety and tolerability of FLT201, and the analysis is summarized in [Section 9](#).

#### **8.3. Secondary Efficacy Endpoint**

Summary tables presenting observed values and changes from baseline for each scheduled post-baseline visit will be presented for the following secondary efficacy endpoints:

- lyso-Gb1 in plasma and DBS
- Spleen volume measured by MRI
- Liver volume measured by MRI
- Hemoglobin level
- Platelet count

The above summaries will be presented by study part, dose cohort, and overall. GCase activity levels in plasma and leukocytes (as well as DBS) are discussed in [Section 10](#).

Additionally, GCase concentrations and the clearance of lyso-Gb1 (plasma and DBS), spleen volume and liver volume will be plotted by-participant over time.

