## **4. General Statistical Considerations**

All study data collected will be presented in data listings, and all relevant data will be tabulated and summarized by study part, dose cohort, and overall, unless stated otherwise.

Continuous data will be described using descriptive statistics (i.e., n, mean, standard deviation, median, minimum, and maximum). Categorical data will be described using the count and percentage in each category. For the summary statistics of all numerical variables unless otherwise specified, minimum and maximum will be displayed to the same level of precision as reported. Mean and median will be displayed to one level of precision greater than the data collected. Standard deviation, standard error, and confidence intervals will be displayed to two levels of precision greater than the data collected.

Missing data will not be imputed. All analyses will be based on observed cases for the safety population unless specified otherwise.

Clinical laboratory and PK results that are below the lower limit of quantification (BLQ/LOQ), below the limit of detection (LOD), above the upper limit of quantification (ULOQ) or missing will be displayed as such in the data listings.

To calculate descriptive statistics and PK parameters, all BLQ, LOQ and LOD results will be treated as half of the BLQ/LOQ/LOD values whereas all ULOQ values will be treated as the ULOQ values as applicable.

The end of the study will be defined as the last visit by the last participant. All participants will be followed up for at least 5 years in a separate long-term follow-up study.

Unless specified otherwise, baseline will be defined as the last non-missing measurement prior to the infusion of IMP.

Change from baseline is defined as: post-baseline value – baseline value.

Study Day 1 is the calendar day of the IMP infusion. Subsequent study days are calculated as the date of assessment/event – date of infusion + 1. Pre-infusion study days are calculated as date of assessment/event – date of infusion. There is no Study Day 0.

All data are summarized based on the visit name collected on the eCRF page.

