### **10.3. Plasma, Leukocyte and DBS Pharmacokinetic Parameters**

Plasma, leukocyte, and DBS GCase baseline adjusted activity level-time data will be analyzed by non-compartmental analysis using Phoenix® WinNonlin® Version 8.3 or higher (Certara USA, Inc., Princeton, NJ). The following PK parameters will be calculated for baseline adjusted GCase activity levels, where data permit:

$C_{\max}$	Maximum observed concentration.
$T_{\max}$	Time of maximum observed concentration.
$AUC_{\text{last}}$	AUC from time 0 to the last measurable observed concentration ( $C_{\text{last}}$ ), calculated using the linear trapezoidal rule.

Actual sampling times will be used for the estimation of all PK parameters, and all available GCaSe activity level data will be included in the analysis (including resulting from samples collected outside predefined collection windows).

Plasma, leukocyte, and DBS PK parameters will be presented in data listings and summarized separately using descriptive statistics (number of observations, arithmetic mean, SD, CV, geometric mean, geometric CV, median, minimum, and maximum) by study part and cohort.  $T_{\max}$  will be summarized using number of observations, median, minimum, and maximum only.

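### SAP 8.3 plans no relative change for lyso-Gb1, spleen volume or liver volume, so in cohorts of one to three the absolute change depends on baseline and can rank doses wrongly on proportional response

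*SAP*

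**What the plan says.** The protocol (Table 3 and section 15.4) makes change from baseline at each assessment a secondary endpoint for plasma lyso-Gb1, spleen volume and liver volume, without fixing a scale.

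The SAP fixes it in section 4: "Change from baseline is defined as: post-baseline value – baseline value". The same section sets the default statistics: "Continuous data will be described using descriptive statistics (i.e., n, mean, standard deviation, median, minimum, and maximum". SAP 8.3 applies both to these endpoints, with lyso-Gb1 in plasma and DBS: "Summary tables presenting observed values and changes from baseline for each scheduled post-baseline visit will be presented for the following secondary efficacy endpoints". The tables are by study part, dose cohort and overall.

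Individual data are also shown. SAP 8.3 adds: "Additionally, GCase concentrations and the clearance of lyso-Gb1 (plasma and DBS), spleen volume and liver volume will be plotted by-participant over time". SAP 4 lists all study data.

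Relative or normalised scales are used elsewhere in the SAP. GCase PK parameters get "geometric mean, geometric CV" (SAP 10.3). Anti-GCase and AAVS3 titres get geometric means and geometric CVs (SAP 12 and 13). Baseline organ size is described as "Screening spleen volume (multiples of normal)" in SAP 6.1, and likewise for the liver. SAP 8.3 states no unit for organ volumes at follow-up.

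**The concern.** Lyso-Gb1 and organ volumes are positive quantities, and a treatment effect on them is naturally read as a proportion. The protocol does so itself: the starting-dose rationale in section 6.5.2 looks for tissue substrate reductions of more than 50% that are also consistent. The SAP plans no group statistic that states a percentage fall or shows how consistent it is.

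The cohorts are very small. Protocol 8.1 plans at least two participants per Part 1 dose, with a possible third. One is enough if GCase activity is below normal and no DLT occurs; expansion beyond three is also allowed. At these sizes one participant's baseline can dominate the mean change, and two cohorts can differ in baseline by chance alone.

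At stake is the reading across doses of the secondary efficacy tables. SAP 8 says the descriptive summaries of these endpoints will also support the EU CTR results summary, so the group figures may travel without the individual plots.

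**Working it through.** The plan has no figure of its own to reproduce: SAP 4.2 bases sample size on feasibility, and no baseline values, effect size or SD are given. The check applies the SAP's definitions to illustrative cohorts. **All baselines and responses below are assumed, in arbitrary units.**

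**Formula.** Let b be a participant's baseline and p the proportional change. The SAP's change is d = b × p. Then

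mean(d) = Σ(b × p)/n = mean(b) × Σ(w × p), with w = b/Σb.

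The mean absolute change is therefore a baseline-weighted average of the proportional changes, multiplied by the mean baseline. Both the weights and the multiplier depend on who was enrolled.

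**1. Comparing two doses, n=2 each, uniform response within each.**

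| Cohort | Baselines | Changes | Mean = median | Min, max | Percent change |
|---|---|---|---|---|---|
| A, 50% fall | 20, 30 | -10, -15 | -12.5 | -15, -10 | -50% |
| B, 20% fall | 100, 150 | -20, -30 | -25 | -30, -20 | -20% |

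B, the weaker proportional response, shows twice the change. The median, minimum and maximum all agree with that order. The observed means do recover the proportions: 12.5/25 = 0.50 and 100/125 = 0.80.

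**2. Consistency within a cohort, n=3, baselines 10, 10, 50, all falling 50%.** The changes are -5, -5, -25, with mean -35/3 = -11.67, SD 11.55 and median -5. Percent change is -50% with SD 0. The participant with the highest baseline supplies 25/35 = 71% of the summed change. The ratio of observed means is 11.67/23.33 = 0.50.

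**3. How the weight depends on baseline spread.** For a uniform 50% fall, the highest-baseline participant's share of the summed change is as follows (for n=3 the other two have equal baselines).

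| Highest/lowest baseline | 1.5 | 2 | 3 | 5 | 10 |
|---|---|---|---|---|---|
| n=2 | 60% | 67% | 75% | 83% | 91% |
| n=3 | 43% | 50% | 60% | 71% | 83% |

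Equal weighting would give 50% and 33%. The distortion is modest at a ratio of 1.5 and large at 5 to 10.

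**4. Mixed response, n=2, baselines 10 and 50; the first falls 50%, the second rises 10%.** The changes are -5 and +5, so mean and median are both 0. The observed means are 30 and 30, ratio 1.00, so here they do not help. Mean percent change is (-50 + 10)/2 = -20%, and the geometric mean ratio is √(0.5 × 1.1) = 0.74. The table's minimum and maximum (-5, +5) do show that the two participants differ.

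**5. Mixed response, n=3, baselines 10, 10, 50; two fall 50%, the highest rises 10%.** The mean change is (-5 - 5 + 5)/3 = -1.67, but the planned median is -5. Mean percent change is -30%, and the geometric mean ratio is (0.5 × 0.5 × 1.1)^(1/3) = 0.65. With three participants the median gives some protection; with two it gives none.

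**The case against.** The strongest reply is that the planned displays already carry the information. Observed values, median, minimum, maximum, by-participant plots and full listings are all planned, and with one to three participants per dose the plots and listings are the natural reading. This largely stands. A reader might infer that only arithmetic means are reported, or that a consistent proportional fall would be hidden. Neither is supported: a uniform fall appears exactly in the ratio of observed means, and every individual change is negative. That ratio is itself baseline-weighted, though, so it fails in the mixed case (step 4). Because missing data are not imputed, the baseline and visit means may also come from different participants.

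Second, nothing formal rests on these endpoints. A reader might want to express the problem as lost power, but SAP 4.2 makes all analysis descriptive, so there is no test for power to describe. The mean also seldom points the wrong way. Assume a 30% true fall, log-normal baselines with CV 50-150% and a log-SD of 0.3 for the individual ratio to baseline. In simulated cohorts of three, the mean change fails to be negative in about 4-6%, against about 2% for the mean log ratio. In cohorts of two the figures are about 6.5-8% and 4.6%. This stands, and it makes the point one of ranking and description.

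Third, neither scale is right in itself. A geometric mean ratio of 0.65 in step 5 would play down the fact that the participant with the highest baseline worsened. Absolute change also follows the protocol's endpoint as the SAP defines it. That is a good reason to keep absolute change and add relative change beside it, without making relative change the lead summary.

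Fourth, a reader might infer that Parts 1 and 2 will be confused, since long-treated and never-treated participants share an overall column. The tables are also given by part and cohort, and protocol section 15 combines parts only where appropriate, so this adds little.

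**Conclusion.** The point holds as a gap in presentation. SAP 4 and 8.3 plan no relative change for lyso-Gb1, spleen volume or liver volume. In cohorts of one to three, the absolute change depends on baseline, and with two participants the median does not correct it. Cohorts with different baselines can be ranked in the wrong order on proportional response (-12.5 for a 50% fall against -25 for a 20% fall). The consistency of a uniform fall is also blurred (SD 11.55 in absolute change, 0 in percent change).

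These sizes rest on assumed baselines. The documents do not give the baseline spread: if it is narrow, the effect is small. The case is stronger for lyso-Gb1 than can be shown for organ volumes, since nothing in the documents indicates that organ volumes vary as widely. It would go too far to say that the effect is hidden or that the tables cannot be compared across doses at all. The observed values, plots and listings allow a careful reader to recover the individual proportions.

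**What to change.** In SAP 8.3, keep the absolute change and add beside it:

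- for lyso-Gb1, plasma and DBS separately, the ratio to baseline at each visit, summarised as geometric mean ratio with geometric CV, plus median percent change;
- for spleen and liver volume, percent change from baseline at each visit;
- a log scale for the by-participant lyso-Gb1 plots already planned.

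Define ratio and percent change in SAP 4 next to the existing definition of change, and state in SAP 8.3 the unit of the follow-up organ volumes.

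The cost is SAP wording and a few extra rows in existing tables. No new data are needed.

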8.1 Study Description

This is a first in human, Phase 1/2, open label, safety, tolerability, and efficacy study in adult patients with Gaucher disease type 1.

Participants will undergo the screening assessments described in Section 12.1.1 and Section 12.1.2. for up to 16 weeks prior to Study Day 1 (gene therapy infusion).

In Part 1, eligible participants currently receiving ERT/SRT will maintain their current treatment until a minimum of 2 consecutive results at least 4 weeks post-dosing show leukocyte GCase activity level higher than pre-dose trough GCase activity level, after which ERT/SRT may be withdrawn.

Progression from Part 1 to Part 2 will be by a substantial protocol amendment, based on safety/tolerability (including DLT), PK, PD, and clinical data.

In Part 2, eligible participants will be PUPs. Participants may need to be considered for initiation of ERT/SRT in case of a lack of a trend to normalisation in leukocyte GCase activity level in serial measurements from at least 4 weeks post-dosing, suggestive of low probability of clinical efficacy.

Treatment-eligible participants will report to the infusion study site on the day prior to receiving the gene therapy infusion (Day -1). Participants will either attend their local study site if it has been approved for FLT201 infusion, or if not, an alternative approved infusion study site. On Day 1, FLT201 will be administered as a single-dose, slow IV infusion into a peripheral vein, and the participant will remain in the study centre for at least 8 hours until the investigator has deemed the participant as fit to be discharged.

Participants will be required to undergo study evaluations at intervals over the 9-month post -treatment period. These will take place either at the study infusion site or at their local study site.

The study will be conducted in 2 parts (Figure 3):

[figure not shown]

Figure 3: Study Schema

Part 1: Dose Escalation in Previously Treated Patients

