11.3.1 Discontinuation/Resumption/Commencement of ERT/SRT

ERT/SRT will be discontinued once GCase activity is in the normal range.

If, after the discontinuation of ERT/SRT, haemoglobin or platelet levels start to decline or if disease-specific biomarkers or other clinical signs and symptoms significantly worsen compared to baseline, then ERT/SRT will be resumed. This information will then inform future decisions for subjects as to the level of GCase activity at which ERT/SRT is to be withdrawn.

In addition, GCase expression loss as evidenced by decline in serial GCase activity measurements to baseline (pre-FLT201 dosing) levels, ERT/SRT will be resumed.

The decision to withdraw or restart ERT/SRT should be discussed with the Medical Monitor and Sponsor.

12 Study Procedures

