**Table 2-2 Secondary Objectives and Endpoints**

Secondary Objectives	Secondary Endpoints
PK: To investigate the relationship of FLT201 dose to endogenous production of GCCase.	Change from baseline to each assessment point in plasma and leukocyte GCCase activity level.
Efficacy: To assess the impact of FLT201 on: 
 
• clearance of lyso-Gb1
 
• spleen size
 
• liver size
 
• hemoglobin
 
• platelet count
 
	Change from baseline to each assessment point in: 
 
• lyso-Gb1 in plasma
 
• spleen volume measured by MRI
 
• liver volume measured by MRI
 
• hemoglobin
 
• platelet count
 

Immunologic: To describe the immune response to GCCase transgene product.	Change from baseline to each assessment point in total anti-GCCase antibody titer and neutralizing antibody titer.
Shedding: To assess viral shedding after systemic administration of FLT201.	Clearance of vector genomes (vg) in plasma, urine, saliva, stool, and semen measured by PCR test.
Abbreviations: GCCase=glucocerebrosidase; lyso-Gb1=glucosylsphingosine; MRI=magnetic resonance imaging; PK=pharmacokinetic; PCR=polymerase chain reaction, vg=vector genomes.	

Table 2-3 presents the exploratory objectives and endpoints.

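### Efficacy values are summarised by visit regardless of ERT/SRT status, so the tables alone cannot separate control by FLT201 alone from control restored by ERT/SRT

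*SAP*

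**What the plan says.** **Analysis.** SAP 8.3 covers lyso-Gb1, spleen volume, liver volume, haemoglobin and platelet count: "Summary tables presenting observed values and changes from baseline for each scheduled post-baseline visit will be presented for the following secondary efficacy endpoints". On grouping it adds: "The above summaries will be presented by study part, dose cohort, and overall". SAP 8.4 handles the exploratory endpoints in the same way. SAP 4 sets the inclusion rule, "All analyses will be based on observed cases for the safety population unless specified otherwise", and the reference point: "baseline will be defined as the last non-missing measurement prior to the infusion of IMP". In SAP Table 2-2 the objective behind the five secondary endpoints begins "To assess the impact of FLT201 on".

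**ERT/SRT during the study.** Under Protocol 8.1, Part 1 participants "will maintain their current treatment until a minimum of 2 consecutive results at least 4 weeks post-dosing" show leukocyte GCase activity above the pre-dose trough; ERT/SRT may then be withdrawn. Part 2 participants may be considered for ERT/SRT if leukocyte GCase does not trend towards normal. Protocol 11.3.1 calls for resumption if haemoglobin or platelets begin to fall, or if disease biomarkers "or other clinical signs and symptoms significantly worsen compared to baseline, then ERT/SRT will be resumed". It also calls for resumption if GCase activity falls back to its pre-dose level.

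**Reporting of ERT/SRT.** Protocol 11.1 has starts, stops and restarts recorded on the Gaucher Treatment eCRF page. SAP 7.1 says "ERT/SRT use will be summarized using Anatomical Therapeutic Chemical (ATC) Level 4", with a listing of all ERT/SRT data. Neither SAP 4, 8.3, 8.4 or 14 nor Protocol 15.4 to 15.6 flags, splits or censors an efficacy value by ERT/SRT status.

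**The concern.** In Part 1 the baseline is itself a value on ERT/SRT, so the hoped-for result after withdrawal is little or no change. A Week 38 mean change near zero fits two opposite histories: FLT201 held the disease alone, or it did not and ERT/SRT was restarted. Resumption is not random. It follows deterioration in some of the same variables, so the participants in whom FLT201 failed are the ones whose later values are repaired.

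Protocol 6.5.3.3 gives freedom from chronic medication as an expected benefit, so this distinction is central to interpreting efficacy. SAP 8 also sends the secondary efficacy summaries into EU CTR results reporting and does not say that the ERT/SRT listing goes with them.

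A related point is the overall column. If it spans both parts, it averages participants stable on ERT/SRT at entry with untreated participants who have room to improve.

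**Working it through.** The plan gives no figure to reproduce. Sample size rests on feasibility (about 12 in Part 1 plus 6 in Part 2, 18 in all), and no resumption rate or off-therapy loss is stated.

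**1. Treatment states entering one visit mean**

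| State | Source | Separated in SAP 8.3 or 8.4? |
|---|---|---|
| FLT201 + continuing ERT/SRT (Part 1) | Protocol 8.1 | No |
| FLT201 alone | Protocol 8.1, 11.3.1 | No |
| FLT201 + resumed ERT/SRT (Part 1) | Protocol 11.3.1 | No |
| FLT201 + newly started ERT/SRT (Part 2) | Protocol 8.1 | No |

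**2. Overlap of endpoints and resumption triggers**

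| Secondary endpoint | Trigger in Protocol 11.3.1? | By-participant plot |
|---|---|---|
| Haemoglobin | Named | SAP 9.2.1 |
| Platelet count | Named | SAP 9.2.1 |
| Lyso-Gb1 | Not named; falls under disease biomarkers (Protocol 13.6 gives it as an example) | SAP 8.3 |
| Spleen, liver volume | Not named | SAP 8.3 |

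The overlap is therefore partial.

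**3. Size at one visit.** Suppose k of n participants lose D off therapy and resume, ERT/SRT restores the whole of D, and the others do not change. Take as target the mean using the resumers' pre-resumption values.

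- Target mean change = −kD/n.
- All-observed mean change = 0.
- Difference = kD/n, too favourable. If only a fraction r of D is restored, the difference is r·kD/n, so kD/n is the upper limit for a given D.

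Shares: 1 of 2 = 0.50D; 1 of 3 = 0.33D; 1 of 12 = 0.08D; 4 of 12 = 0.33D.

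For haemoglobin, with D assumed to be 0.5 to 2.0 g/dL:

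| Resumed | All-observed mean (g/dL) | Mean with pre-resumption values (g/dL) |
|---|---|---|
| 1 of 2 | 0.00 | −0.25 to −1.00 |
| 1 of 3 | 0.00 | −0.17 to −0.67 |
| 2 of 12 | 0.00 | −0.08 to −0.33 |

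**4. Chance that it arises.** With assumed resumption probability p, P(at least one) = 1 − (1 − p)^n. For p from 0.10 to 0.50 this is 0.27 to 0.88 for n = 3, and 0.72 to nearly 1 for n = 12.

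**5. Would dropping post-resumption values cure it?** No. With n = 3 and k = 1, the two remaining participants give (0 + 0)/2 = 0. The target is −D/3, so the error is again D/3: only participants who did not fail are left.

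**6. When off-ERT/SRT time begins.** Protocol 8.1 asks for two consecutive leukocyte GCase results above the pre-dose trough, at Week 4 or later. With weekly sampling, the earliest withdrawal is about Week 5. Protocol 11.3.1 stops ERT/SRT once GCase activity is in the normal range, with no minimum time. The criteria differ, so the start of off-ERT/SRT time is not fixed by the documents.

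**The case against.** **The planned outputs already show the data.** All ERT/SRT use is listed, and all five secondary endpoints have by-participant plots. With 2 or 3 participants per cohort, a careful reader could line these up. This stands as a limit on the harm: a reader might infer that ERT/SRT appears only as a drug-class table, and that is not so. But the cross-check is manual, no plot is specified to mark ERT/SRT periods, and no planned output counts who was off ERT/SRT at a visit.

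**The SAP makes no attribution claim.** A reader might infer that restored values are formally credited to FLT201. The documents do not support this: the study is single-arm, all analysis is descriptive, and SAP 8.3 follows the protocol's endpoint wording. What remains is that the tables serve an objective about the impact of FLT201 and cannot isolate it.

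**The size is assumed.** This stands. Neither k nor D is in the documents, and full restoration within 38 weeks is not assured: Protocol 6.1 describes benefit from standard therapy over 2 to 5 years and incomplete response in some patients.

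**The overall column may be harmless.** Protocol 15 reports parts separately and combines them where appropriate, with safety as its example; Part 2 also needs an amendment first. This largely answers the point, but SAP 8.3 does not repeat the limit for efficacy.

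**Conclusion.** The point holds as a gap in the SAP. Visit summaries of efficacy pool values on and off ERT/SRT, and resumption is triggered partly by haemoglobin, platelets and disease biomarkers. From the tables alone, stability at a late visit cannot be read as control by FLT201 alone. For a given loss D the visit mean is too favourable by up to kD/n: D/2 for 1 of 2 and D/3 for 1 of 3. This assumes full restoration and takes the pre-resumption value as the target.

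A reader might also infer that every Week 4 lyso-Gb1 value is measured on ERT/SRT. That follows only if Protocol 8.1 governs; 11.3.1 sets no minimum time.

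The severity is should-fix. The primary endpoint is safety, these endpoints are secondary or exploratory, and no test, error rate or decision threshold depends on them.

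**What to change.** Keep the all-observed table, and say in SAP 8.3 and 8.4 that it describes values regardless of ERT/SRT use. Derive ERT/SRT status at each visit from the Gaucher Treatment eCRF page and add, by cohort:

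1. The same summaries split by on and off ERT/SRT, with the number off ERT/SRT at each visit.
2. The number withdrawing, resuming (Part 1) or initiating (Part 2) ERT/SRT, and time to resumption.
3. Each resumer's last value before resumption, with change from baseline and from the last value before withdrawal. Add a sensitivity summary that uses the pre-resumption value at later visits. The SAP must specify this explicitly, because its default is observed cases without imputation. Do not rely on deleting post-resumption values, for the reason in step 5 of the working.
4. ERT/SRT periods marked on the by-participant plots.

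Restrict any overall efficacy column to within each study part, in line with Protocol 15. Reconcile the withdrawal criteria in Protocol 8.1 and 11.3.1, since they set when off-ERT/SRT time begins.

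The cost is SAP wording, one derived variable and extra tables; no new data collection is needed. Off-ERT/SRT denominators will be small, sometimes one participant or none, so those cells should be read as individual values. The sensitivity summary carries a value forward and is itself an assumption.
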